3.4.4 Exploratory Endpoints

The immunogenicity parameters will be calculated with their 95% CIs using the exact binomial distribution (Clopper-Pearson method) for proportions and using normal approximation of log-transformed for GMTs. All analyses will be conducted by study group. The main parameters will also de described by age subgroup. For some parameters (eg. GMTs, 4-fold rise) difference or ratio between groups may be calculated with 95%CI. The 95% CI of ratios of GMTs will be calculated using normal approximation of log-transformed titers and those for proportions difference (ie, 4-fold rise) will be calculated using Wilson Score method without continuity correction.

Neutralizing Ab titers will be measured for each influenza strain with the SN method.

In particular, the following endpoints will be described with 95% CIs:

- GMTs of individual SN antibody (Ab) titer on D01 and 28 days after vaccination (D29)
- GMs of individual SN Ab titer ratio (fold increase in post-vaccination titer relative to D01) at 28 days after vaccination (D29)
- Percentage of participants with SN Ab titers \geq 20 (1/dil), \geq 40 (1/dil), \geq 80 (1/dil) at 28 days after vaccination (D29)

• Percentage of participants with fold-increase in SN Ab titer (post/pre) ≥ 2 and ≥ 4 at 28 days after vaccination (D29)

SAP Core Body: VAP00027

- Percentage of participants with detectable SN Ab titer (SN Ab titer ≥ 10 [1/dil]) at D01 and 28 days after vaccination (D29)
- The RCDCs of pre-vaccination titer (D01) and post-vaccination titer (D29) will be generated for each study group. The RCDCs will include the plots of the 2 groups on the same figure.

In addition, the descriptive summary of SN immunogenicity results will also be produced by:

- Serological SN status at baseline (< 10 and ≥ 10 1/dil)
- Previous influenza vaccination status
- Age subgroup
- Sex
- Race

The analysis will be conducted for each immunogenicity variable on the PPAS subset (PPAS-SN) and on the FAS subset (FAS-SN) if the attrition rate from FAS-SN to PPAS-SN is greater than 10%.

3.4.5 Handling of Missing Data and Outliers

3.4.5.1 Safety

Generally, no replacement will be done for Safety Missing Data and Outliers.

3.4.5.1.1 Immediate

For unsolicited systemic AEs, a missing response to the "Immediate" field is assumed to have occurred after the 30-minute surveillance period and will not be imputed.

3.4.5.1.2 Causal Relationship

By convention, all events reported at the injection site (either solicited or unsolicited) will be considered as related to the administered product and then referred to as reactions. In a same way, all solicited systemic events pre-listed in the CRF are also considered as related to vaccination and will be considered as reactions.

- For unsolicited systemic AE, missing relationship will be considered as related to study vaccine(s) at the time of analysis.
- The missing relationship to study procedures for SAEs will not be imputed.

3.4.5.1.3 Intensity

For solicited reactions, missing intensities will be handled as described in Section 4.2.1.1.1. For unsolicited AEs, missing intensities will remain missing and will not be imputed.

3.4.5.1.4 Start Date and End Date

Missing or partially missing start dates or end dates for unsolicited AEs (including SAEs) will remain missing and not be imputed. If the start date is missing or partially missing, the time of onset will be considered missing. If either the start date or end date is missing or partially missing, the duration will be considered missing.

SAP Core Body: VAP00027

Missing or partially missing end dates for ongoing solicited AEs will remain missing and not be imputed.

3.4.5.1.5 Action Taken

Missing actions taken will remain missing and not be imputed.

3.4.5.2 Immunogenicity

No imputation of missing values and no search for outliers will be performed. LLOQ and ULOQ management will be performed as described in Section 4.2.3.1.

3.5 Interim Analysis

The statistical analysis will be performed as follows:

- An interim analysis on immunogenicity focused on the HAI data to address the primary objective and safety results obtained on data collected within 28 days after vaccination (from D01 to D29).
- A final analysis will be performed after the SN data are available and the 6-month safety follow-up data have been collected.

No statistical adjustment for the interim analysis is necessary because there are no repeat analyses of the same hypotheses.

3.6 Data Monitoring Committee (DMC)

No independent Data Monitoring Committee (DMC) is planned.

Participant safety data will be continuously monitored by the Sponsor's internal safety management team (SMT), led by the Global Safety Officer, to detect any safety signals during the study period.

In addition, this study will include an early safety data review (ESDR), when at least 10% of subjects have been vaccinated and provided safety data for 7 days after vaccination.

A separate SAP will be dedicated to this analysis.

4 Complementary Information on Assessment Methods

4.1 Complementary Information for Endpoints Assessment Methods

Not applicable.

4.2 Complementary Information on Derived Endpoints: Calculation Methods

SAP Core Body: VAP00027

4.2.1 Safety

4.2.1.1 Solicited Reactions

4.2.1.1.1 Daily Intensity

All daily records for solicited reactions will be derived into daily intensity according to the following classification: None, Grade 1, Grade 2, Grade 3, or Missing (Unknown).

For the derivation of daily intensities, the following sequential steps will be applied:

- 1) Solicited reactions (except Fever/Pyrexia) with CRF presence recorded as "No" and with all daily records missing (Unknown) then all daily intensities will be derived as None.
- 2) For non-measurable solicited reactions, daily intensities will correspond to daily records reported in the clinical database. For measurable solicited reactions the daily measurements reported in the clinical database will be converted based upon the intensity scales defined in the protocol; this assumes a reaction that is too large to measure (non-measurable, "NM") is Grade 3. Note: the intensity could be considered "None" (not a reaction) in the analysis despite being considered a reaction by the investigator (e.g., swelling measurement > 0 mm but < 25 mm in adults).

Note: The maximum intensity on the ongoing period is derived from the record of the maximum intensity/measurement after the end of the solicited period following the rule described above.

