3.4.3 Secondary Endpoints

Immunogenicity

success.

The immunogenicity parameters will be calculated with their 95% CIs using the exact binomial distribution (Clopper-Pearson method) for proportions and using normal approximation of log-transformed for GMTs and GMTs ratio. The 95% CI of proportions difference (ie, difference between vaccine groups in SC) will be calculated using Wilson Score method without continuity correction. All analyses will be conducted by study group.

The following descriptive statistics will be displayed:

- GMTs of individual-HAI titer on D01 and 28 days after vaccination (D29)
- Percentage of participants with detectable HAI titer, ie, with a titer ≥ 10 (1/dil) at D01 and 28 days after vaccination (D29)
- GMs of individual titer ratio: 28 days after vaccination (D29) /D01
- Percentage of participants with titer ≥ 40 (1/dil) on D01 and 28 days after vaccination (D29)
- SC rates (titer < 10 [1/dil] at D01 and post-injection titer ≥ 40 (1/dil) at D29 or titer ≥ 10 (1/dil) at D01 and a ≥ 4-fold rise in titer (1/dil) at D29)
- The RCDCs of pre-vaccination titer (D01), and post-vaccination titer (D29) will be generated for each study group. The RCDCs will include the plots of the 2 study groups the same figure.

The analysis will be conducted for each immunogenicity variable on the PPAS, and on FAS if the attrition rate from FAS to PPAS is greater than 10%.

In addition, subgroup analyses will be performed; in particular, immunogenicity will be described according to age subgroups (9-11y, 12-17y, 18-34y and 35-49y), sex, race, previous influenza vaccination status (received a seasonal influenza vaccine in the last past influenza season or not) and baseline seropositivity status (seropositive and seronegative are defined as baseline antibody titer $\geq 1:10$ or < 1:10)., as appropriate according to number of participants in the respective subgroups.

Safety

For the main safety parameters, 95% CIs of point estimates will be calculated using the exact binomial method (Clopper-Pearson method) for single proportions and using the normal approximation for quantitative data.

SAP Core Body: VAP00027

All analyses will be descriptive; no hypotheses will be tested.

The number of participants with documented safety will be used as denominator of the frequencies.

For solicited reactions, the denominator will be the total number of participants who have non-missing data for the endpoint considered

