4.2.1.1.3 Presence

Presence is derived from the maximum overall intensity over the time period considered:

- None: No presence
- Grade 1, Grade 2, or Grade 3: Presence

• Missing or Unknown: Missing presence

Participants with at least one non-missing presence for a specific endpoint will be included in the analysis. Conversely, those without a non-missing presence will not be included in the analysis of the endpoint.

SAP Core Body: VAP00027

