4.2.1.2 Unsolicited AEs

4.2.1.2.1 Presence

An observation will be considered an event if it has at least a verbatim term and is not a Grade 0 intensity event.

SAP Core Body: VAP00027

Grade 0 events are not included in safety analysis but are included in separate listings.

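### SAP 4.2.1.1.1 uses a CRF 'No' when all daily records are missing but not a CRF 'Yes', so recorded solicited reactions drop out wherever such records occur

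*SAP*

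**What the plan says.** SAP 4.2.1.1.1 derives daily intensities in two sequential steps.

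- Step 1 applies to "Solicited reactions (except Fever/Pyrexia) with CRF presence recorded as" 'No'. In full, the condition and result are: "CRF presence recorded as 'No' and with all daily records missing (Unknown) then all daily intensities will be derived as None".
- Step 2 takes intensity from the database only. "For non-measurable solicited reactions, daily intensities will correspond to daily records reported in the clinical database". For measurable reactions, the recorded measurement is converted using the protocol's intensity scale.

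SAP 4.2.1.1.2 takes the maximum of the daily intensities. SAP 4.2.1.1.3 derives presence from that maximum, with "Missing or Unknown: Missing presence", and continues: "Conversely, those without a non-missing presence will not be included in the analysis of the endpoint". SAP 3.4.3 sets the denominator to match: "For solicited reactions, the denominator will be the total number of participants who have non-missing data for the endpoint considered".

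The missing-data section adds no further rule. SAP 3.4.5.1.3 says: "For solicited reactions, missing intensities will be handled as described in Section 4.2.1.1.1".

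Unsolicited events are handled differently. Under SAP 4.2.1.2.1 an observation is an event "if it has at least a verbatim term and is not a Grade 0 intensity event", and SAP 3.4.5.1.3 leaves a missing unsolicited intensity as missing. An unsolicited event with no grade is therefore still counted.

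**The concern.** The CRF presence field is an answer collected by the site. The SAP relies on it when it says 'No' and ignores it when it says 'Yes', although the daily records are equally absent in both cases. A recorded non-reaction stays in the denominator, while a recorded reaction leaves both numerator and denominator.

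The case can arise. Protocol 8.3.2 has the site interview the participant, clarify incomplete diaries and enter information that the diary lacks, so a reaction can be reported without day-by-day grades. Step 1 itself anticipates a presence answer with no daily records.

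A non-serious reaction lost this way is not picked up elsewhere. Under Protocol 10.2.1, an event that meets the solicited conditions is not an unsolicited AE, and solicited reactions are excluded from MAAEs.

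Solicited reactions belong to the key secondary safety objective and are described by age group, in a study meant to support extending the indication to ages 9-17.

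**Working it through.** Neither document states a figure that depends on this rule, so there is none to reproduce. The check is a trace of the rules followed by algebra.

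**Trace, one reaction other than fever, all daily records missing**

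| CRF presence | Step 1 | Step 2 | Maximum | Presence | In the endpoint? |
|---|---|---|---|---|---|
| 'No' | all days None | – | None | No | Yes, as a non-event |
| 'Yes' | does not apply | nothing to convert, stays Missing | Missing | Missing | No |

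The second row is what the steps produce when applied in order. No sentence names that case.

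**Algebra.** Let a = 'Yes' with at least one graded day, b = 'Yes' with no daily records, c = 'No'.

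- Rate under the SAP: a/(a+c)
- Rate with every 'Yes' counted: (a+b)/(a+b+c)
- Difference: −bc/[(a+c)(a+b+c)]. This is negative when b and c both exceed 0, and zero when b = 0.

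Let p be the rate with every 'Yes' counted and f the share of 'Yes' participants with no daily records. The SAP rate is then p(1−f)/(1−pf).

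**Inputs.** N = 667 per age group (SAP Table 1.1). For scale, p = 37% for injection site pain, 20% for headache and 13% for myalgia. These are adult rates from the earlier trial cited in Protocol Table 2.1. The value of f is not in the documents, so a range is shown.

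**Example, pain, f = 5%.** There are 0.37 × 667 = 246.8 'Yes' participants, of whom 12.3 lack records. So a = 234.4, c = 420.2, and the SAP rate is 234.4/654.7 = 35.8%, against 37.0%.

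| f | Pain: SAP rate (dropped) | Shift, pain 37% | Shift, headache 20% | Shift, myalgia 13% |
|---|---|---|---|---|
| 0 | 37.0% (0) | 0 | 0 | 0 |
| 1% | 36.8% (about 2) | −0.23 | −0.16 | −0.11 |
| 5% | 35.8% (about 12) | −1.19 | −0.81 | −0.57 |
| 10% | 34.6% (about 25) | −2.42 | −1.63 | −1.15 |
| 20% | 32.0% (about 49) | −5.03 | −3.33 | −2.32 |

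Shifts are in percentage points.

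**Where the algebra applies.** It needs every 'Yes' to be an event under the SAP's own scale. Protocol Tables 10.1 to 10.3 give this for pain, headache, malaise, myalgia and chills. They also give it for induration and bruising at all ages, where Grade 1 starts above 0 mm, and for erythema and swelling at ages 9-11 for the same reason. It does not hold in two places:

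- Erythema and swelling at 12 years and over: Grade 1 starts at 25 mm, and SAP 4.2.1.1.1 says a smaller measurement can be analysed as None. An unmeasured 'Yes' may be a non-event. Dropping k non-events turns e/n into e/(n−k), which is higher.
- Fever: it is exempt from step 1, so 'No' and 'Yes' are not treated differently, and the temperature defines the reaction.

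**Would dropping the 'No' cases restore balance?** Not reliably. For pain with f = 5%, dropping 0, 5, 10 or 50% of the 'No' group gives 35.8, 37.0, 38.3 or 52.7%. The error can turn upward.

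**The case against.** The strongest reply is that the gap may be empty. No sentence says that a 'Yes' without daily records is excluded; this follows only from chaining the steps. The missing item is the daily record in the clinical database, not necessarily a blank diary. Site interview (Protocol 8.3.2) and database cleaning before lock (Protocol 9.4.1) should fill many such records. Restricting the denominator to non-missing data is prespecified, and SAP 3.4.5.1 says missing safety data are generally not replaced. Safety is descriptive. Shifts of about a point are also small beside sampling error: at n = 667 the normal-approximation 95% half-width is 1.96 × √(0.37 × 0.63/667), or about 3.7 points.

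Much of this stands. The documents do not show that any such records exist, and the 'No' rule is sound because a 'No' is collected information. What does not stand is the appeal to non-replacement. Counting a recorded 'Yes' imputes nothing: the grade stays missing and only the answer already given is used. A shift in one direction is also not sampling error, and the interval does not allow for it.

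A reader might go further and infer three things that the documents do not support:

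- That the rule can only lower rates. This fails for unmeasured erythema and swelling at 12 years and over, as shown above.
- That a composite such as any systemic reaction scores a known reactor as None. SAP 4.2.1.1.2 and 4.2.1.1.3 give no rule for taking the maximum across reactions, so this is open rather than stated.
- That the age-group description is distorted. That depends on how many 'Yes' answers lack daily records in each group, which is not given.

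**Conclusion.** The concern holds as a conditional one. The written steps remove a recorded reaction from its endpoint when all daily records are missing, while keeping a recorded non-reaction. Wherever this happens, the any-grade rate is biased downward for pain, headache, malaise, myalgia, chills, induration and bruising at all ages, and for erythema and swelling at ages 9-11. A flat statement that the trial's solicited rates are biased downward would go too far, because the bias is zero if no such records exist.

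The size rests on an assumed share of 'Yes' participants without daily records. At 1-5% the shift is about 0.2-1.2 points for a 37% rate, and less for the 20% and 13% rates. The non-inferiority analyses of HAI titers and seroconversion, and their power, are unaffected. The change is still worth making: the outcome is key secondary, the lost information has already been collected, and the SAP already counts ungraded unsolicited events.

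**What to change.** Leave step 1 as it is and make four changes.

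1. Add a step to SAP 4.2.1.1.1. For pain, headache, malaise, myalgia, chills, induration and bruising at all ages, and erythema and swelling at ages 9-11, CRF presence 'Yes' with all daily records missing gives maximum intensity Missing and presence Yes.
2. Add a matching line to SAP 4.2.1.1.3, so that these participants count in the numerator and denominator of the any-grade rate and appear in a 'grade missing' row.
3. For fever, and for erythema and swelling at 12 years and over, keep Missing, and report the number of such 'Yes' records by endpoint and age group.
4. State that a composite endpoint is not scored None for a participant with such a 'Yes'.

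The cost is a few sentences in the SAP and a few lines of programming. Where such records exist, the reported rates become slightly less favourable.

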10.2.5.1 Tables for Clinical Abnormalities

10.2.5.1.1 Solicited AR Intensity Grading Scale

Table 10.1: Solicited injection site reactions: terminology, definitions, and intensity scales – Children aged 2 through 11 years

CRF term (MedDRA lowest level term [LLT])	Injection site pain	Injection site erythema	Injection site swelling	Injection site induration	Injection site bruising
Diary card term	Pain	Redness	Swelling	Hardening	Bruising
Definition	Pain either present spontaneously or when the injection site is touched or injected limb is mobilized	Presence of a redness including the approximate point of needle entry	Swelling at or near the injection site Swelling or edema is caused by a fluid infiltration in tissue or cavity and, depending on the space available for the fluid to disperse, swelling may be either soft (typically) or firm (less typical) to touch and thus can be best described by looking at the size of the swelling	Hardening at or near the injection site. Hardening is caused by a slow diffusion of the product in the tissue leading to a thick or hard area to touch at or near the injection site and thus can be best described by looking at the size of the hardening.	Bruising is the result of the diffusion of blood in the skin from ruptured blood vessels that forms a purple or black and blue spot on the skin. It can be best described by looking at its size.
Intensity scale*	CRF:	Grade 1: > 0 to	Grade 1: > 0 to < 25 mm	Grade 1: > 0 to < 25 mm	Grade 1: > 0 to < 25 mm
	Grade 1: Easily tolerated	< 25 mm	Grade $2: \ge 25$ to < 50 mm	Grade $2: \ge 25$ to < 50 mm	Grade $2: \ge 25$ to < 50 mm
	Grade 2: Sufficiently discomforting to interfere with normal behavior or activities	Grade $2: \ge 25$ to < 50 mm Grade $3: \ge 50$ mm	Grade 3: ≥ 50 mm	Grade 3: ≥ 50 mm	Grade 3: ≥ 50 mm
	Grade 3: Incapacitating, unable to perform usual activities				

Diary card:		
Grade 1: No interference with activity		
Grade 2: Some interference with activity		
Grade 3: Significant; prevents daily activity		

VAP00027

Protocol Version 2.0

MedDRA: Medical Dictionary for Regulatory Activities

^{*} For pain, the scale will be provided in the CRF and the intensity will be transcribed from the diary card. For other injection site reactions (erythema and swelling), the classification as Grades 1, 2, or 3 will be applied at the time of statistical analysis; the scale is provided for information purposes only. The actual size of the reaction will be reported in the CRF.

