Table 10.2: Solicited injection site reactions: terminology, definitions, and intensity scales – Adolescents and adults aged≥ 12 years

CRF term (MedDRA lowest	Injection site pain	Injection site erythema	Injection site swelling	Injection site induration	Injection site bruising
level term [LLT])	Da:	·	Constline	Handanin a	Desirie
Diary card term	Pain	Redness	Swelling	Hardening	Bruising
Definition	Pain either present spontaneously or when the injection site is touched or injected limb is mobilized	Presence of a redness including the approximate point of needle entry	Swelling at or near the injection site Swelling or edema is caused by a fluid infiltration in tissue or cavity and, depending on the space available for the fluid to disperse, swelling may be either soft (typically) or firm (less typical) to touch and thus can be best described by looking at the size of the swelling	Hardening at or near the injection site. Hardening is caused by a slow diffusion of the product in the tissue leading to a thick or hard area to touch at or near the injection site and thus can be best described by looking at the size of the hardening.	Bruising is the result of the diffusion of blood in the skin from ruptured blood vessels that forms a purple or black and blue spot on the skin. It can be best described by looking at its size.

Intensity	CRF:	Grade 1:	Grade 1: \geq 25 to \leq 50 mm	Grade 1: > 0 to < 25 mm	Grade 1: > 0 to < 25 mm
scale*	Grade 1: A type of adverse event that is	\geq 25 to	Grade $2: \ge 51$ to ≤ 100 mm	Grade 2: \geq 25 to \leq 50 mm	Grade $2: \ge 25$ to < 50 mm
	usually transient and may require only	≤ 50 mm	Grade 3: > 100 mm	Grade $3: \ge 50 \text{ mm}$	Grade $3: \ge 50 \text{ mm}$
	minimal treatment or therapeutic	Grade 2:			
	intervention. The event does not generally	\geq 51 to			
	interfere with usual activities of daily	$\leq 100 \text{ mm}$			
	living.	Grade 3:			
	Grade 2: A type of adverse event that is	> 100 mm			
	usually alleviated with additional				
	therapeutic intervention. The event				
	interferes with usual activities of daily				
	living, causing discomfort but poses no				
	significant or permanent risk of harm to				
	the research participant.				
	Grade 3: A type of adverse event that				
	interrupts usual activities of daily living, or				
	significantly affects clinical status, or may				
	require intensive therapeutic intervention.				
	Diary card:				
	Grade 1: No interference with activity				

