^{§§} To comply with US Food and Drug Administration (FDA) expectations, Sponsors are to enroll participants who reflect the demographic for clinically relevant populations with regards to age, gender, race, and ethnicity (FDA. Collection of race and ethnicity data in clinical trials: Guidance for industry and Food and Drug Administration staff [Internet]. 2016. Available from: https://www.fda.gov/media/75453/download)

^{***}Including history of laboratory-confirmed influenza illness over the previous 3 influenza seasons.

2 Objectives and Endpoints

Table 2.1: Objectives and endpoints

Objectives	Endpoints
Primary	
To demonstrate the non-inferior hemagglutination inhibition (HAI) immune response of quadrivalent recombinant influenza vaccine (RIV4) for the 4 strains in participants aged 9 to 17 years vs participants aged 18 to 49 years	 Individual HAI titer 28 days after vaccination (D29) Seroconversion (SC) (titer < 10 [1/dil] at D01 and post-injection titer ≥ 40 [1/dil] at D29, or titer ≥ 10 [1/dil] at D01 and a ≥ 4-fold rise in titer [1/dil] at D29)
Key Secondary	
To summarize the HAI immune response induced by RIV4 in all participants.	 Individual-HAI titer on D01 and 28 days after vaccination (D29) Detectable HAI titer, ie, with a titer ≥ 10 (1/dil) at D01 and 28 days after vaccination (D29) Individual titer ratio: 28 days after vaccination (D29) /D01 Participants with titer ≥ 40 (1/dil) on D01 and 28 days after vaccination (D29) SC (titer < 10 [1/dil] at D01 and postinjection titer ≥ 40 (1/dil) at D29 or titer ≥ 10 (1/dil) at D01 and a ≥ 4-fold rise in titer (1/dil) at D29)
To describe the safety profile of RIV4 vaccine in all participants and by age group	 Occurrence of any unsolicited systemic adverse events (AEs) reported in the 30 minutes after vaccination Occurrence of solicited (pre-listed in the participant's diary card [DC]/electronic diary card [eDC] and case report book [CRB]) injection site reactions and systemic reactions occurring up to 8 days after vaccination Occurrence of unsolicited AEs up to 28 days after vaccination

SAP Core Body: VAP00027

	 Occurrence of medically attended adverse events (MAAEs) up to 28 days after vaccination Occurrence of serious adverse events (SAEs) (including adverse events of special interest [AESIs]) throughout the study Occurrence of AESIs throughout the study
Exploratory	

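### Erythema and swelling count as present from above 0 mm at ages 9-11 but only from 25 mm at age 12 and over, so the pooled 9-17 and all-participant rates mix two definitions

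*SAP*

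**What the plan says.** Protocol section 10.2.5.1.1 has two scales for solicited injection site reactions.

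- Table 10.1, headed "Children aged 2 through 11 years", covers this trial's 9-11 year-olds. Erythema and swelling are "Grade 1: > 0 to < 25 mm", Grade 2 from 25 to below 50 mm, and Grade 3 from 50 mm.
- Table 10.2, headed "Adolescents and adults aged≥ 12 years", covers ages 12-17 and all adults. For the same two reactions Grade 1 runs from 25 to 50 mm, Grade 2 from 51 to 100 mm, and the top category is "Grade 3: > 100 mm".

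Induration and bruising start at Grade 1 above 0 mm in both tables, so the difference in presence is confined to erythema and swelling. The footnotes to both tables add: "The actual size of the reaction will be reported in the CRF".

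SAP 4.2.1.1.1 converts each daily measurement to a grade on the protocol scales. It warns that the result can be no reaction even where the investigator recorded one, and gives as its example a "swelling measurement > 0 mm but < 25 mm in adults". SAP 4.2.1.1.3 then sets presence to yes only for Grade 1 or higher.

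The study groups are 9-17 and 18-49 years (SAP 4.2.4.1). The safety objective in SAP Table 2.1 is "To describe the safety profile of RIV4 vaccine in all participants and by age group". SAP 3.4.3 also plans the main safety endpoints by 9-11, 12-17, 18-34 and 35-49 years, where numbers allow. Safety is descriptive throughout.

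**The concern.** For these two reactions, age decides whether the endpoint occurred, not only how severe it was. A 10 mm swelling is present in an 11-year-old and absent in a 12-year-old. A 60 mm swelling is Grade 3 in the first and Grade 2 in the second.

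The 9-17 group spans that boundary, while the adult group lies wholly on the 25 mm scale. A pooled 9-17 rate is therefore a weighted mixture of two different quantities, and so is the all-participant rate. A reader who sets the 9-17 row beside the 18-49 row could take a difference in cut-off for a difference in reactogenicity. The direction is known: the mixture raises the paediatric rate. The study is meant to support extending the indication to this age range, so the descriptive rates should be readable as one quantity.

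**Working it through.** The documents state no erythema or swelling rate, so there is no planned figure to reproduce. The check follows the definitions and then works out how large the artefact can be.

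**Inputs from the documents**
- Presence cut-off: above 0 mm at ages 9-11 (Protocol Table 10.1) and 25 mm at age 12 and over (Table 10.2).
- Share aged 9-11 in the 9-17 group: c of at least 0.30, with no upper limit stated (Protocol 1.1).
- Group sizes: 667 and 667 (Protocol 1.1).

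**Assumptions, not in the documents**
- The true distribution of reaction size is the same at every age.
- s = P(largest size above 0 and below 25 mm).
- L = P(largest size 25 mm or more).

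**Formulas**
- Ages 9-11: s + L. Ages 12-17 and adults: L.
- Pooled 9-17: c(s + L) + (1 − c)L = L + c·s.
- Spurious difference, 9-17 minus adults: (L + c·s) − L = c·s. It does not depend on L.
- All participants, with equal groups: L + c·s/2.

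**Results at c = 0.30**

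| s | L | 9-11 | 12-17 and adults | Pooled 9-17 | All | 9-17 minus adults, points (95% CI) |
|---|---|---|---|---|---|---|
| 2% | 1% | 3.0% | 1.0% | 1.6% | 1.3% | 0.6 (−0.7 to 2.0) |
| 5% | 2% | 7.0% | 2.0% | 3.5% | 2.75% | 1.5 (−0.3 to 3.4) |
| 10% | 3% | 13.0% | 3.0% | 6.0% | 4.5% | 3.0 (0.8 to 5.3) |
| 20% | 5% | 25.0% | 5.0% | 11.0% | 8.0% | 6.0 (3.1 to 9.0) |

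For s = 10%, for example, the pooled rate is 0.30 × 13.0% + 0.70 × 3.0% = 6.0%, against 3.0% in adults. The intervals use the Newcombe-Wilson method at 667 per group. The plan specifies no such contrast for safety; they show only when the artefact could pass for a real difference.

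Because 30% is a minimum, c can be larger. At c = 0.50 the artefact is 1.0, 2.5, 5.0 and 10.0 points for the same four values of s.

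With one cut-off at every age the artefact is zero. For s = 10% and L = 3%, both study groups show 13.0% at above 0 mm, or 3.0% at 25 mm.

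The same reasoning applies to Grade 3, where the affected band is 50 to 100 mm: the artefact is c times the proportion whose largest size falls in that band.

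**The case against.** The strongest reply is that this is a disclosed choice. The scales are set out by age in two titled tables, the protocol says they are adapted from a regulatory grading guidance, and the SAP states the consequence for small adult reactions. That stands, and nothing here asks for the grading to change.

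The second reply is that the age-subgroup tables already deal with it. Each of the four bands uses a single scale. At least 30% of 667 is about 200 children aged 9-11, so the numbers proviso is unlikely to remove that band. A reader can compare 12-17 with adults directly. This limits the problem but leaves the 9-17 and all-participant rows mixed. On its own it also shows a step between 9-11 and 12-17 that the cut-off may have created.

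Third, the supplied SAP is a core body without table shells, so a footnote may exist elsewhere. That is possible. What can be said is that neither document plans a common cut-off or a caution on the pooled rows.

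Some stronger readings are tempting but not supported:

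- *That no paediatric rate can be compared with adults.* The 12-17 rates share the adult scale.
- *That a planned safety comparison is biased.* The plan describes safety by group, tests no safety hypothesis and specifies no between-group safety difference.
- *That the any-injection-site-reaction row is materially distorted.* For presence, that row changes only for 9-11 year-olds whose sole reaction is erythema or swelling below 25 mm. Pain, induration and bruising are counted as present on the same basis at all ages, and the protocol's account of the earlier adult trial has tenderness (48%) and pain (37%) as the leading injection site symptoms. The effect is probably small.
- *That the early safety data review is undermined.* It concerns ages 9-17 only, prompts a sponsor decision rather than an automatic pause, and has its own SAP, which was not supplied. The change proposed here would not alter it, so it forms no part of this point.

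**Conclusion.** The point holds for the descriptive erythema and swelling rates, both presence and Grade 3. The pooled 9-17 and all-participant rows mix two definitions, and the 9-11 and pooled 9-17 rates are not like-for-like with adults.

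The size depends on s, which the documents do not give. At the minimum 30% share of 9-11 year-olds, the artefact is under 2 points if small reactions are uncommon (s of 5% or less) and reaches 6.0 points at s = 20%. These figures assume the same true size distribution at every age. If the true distributions differ, the artefact adds to the real difference, and the planned pooled rows cannot separate the two.

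The primary non-inferiority objective is untouched. No information is lost, because the sizes are recorded. This is a matter of presentation in secondary safety results, worth correcting because the correction is cheap.

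**What to change.** Keep the age-specific grading as it is. In SAP 3.4.3, add one supplementary descriptive table of erythema and swelling for 9-17, 18-49 and all participants, using the same millimetre cut-offs at every age: above 0, 25 or more, 50 or more, and above 100 mm. Build it from the sizes already in the CRF. State that any descriptive remark comparing age groups on these two reactions will rest on that table. Footnote the pooled 9-17 and all-participant rows in the standard tables to say that they combine two grading scales.

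The cost is one extra table and a footnote, with no new data or procedures. The drawback is a second set of rates to explain beside the graded ones.
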